16.3 In vitro hematopoietic colony formation

Bone marrow aspirates will be collected as per the study calendar (page 36). Mononuclear cells from frozen aspirate from CMML subjects will be plated in methylcellulose for 14 days. Experimental Conditions will include no cytokine, GM-CSF, and with or without increasing doses of ruxolitinib. Colonies will be counted after 14 day and experimental conditions will be compared to evaluate ruxolitinib efficacy. The colony formation assay described remains the gold standard for *in vitro* differentiation and proliferation experiments in hematopoetic precursors. Our laboratory has been able to plate previously frozen cells with

GM-CSF inhibitors and detect differences in colony numbers. The vast majority of colonies detected in our preliminary data are of the GM-CFU type with an occasional GEMM-CFU colony. Our colony "read out" is defined as any hematopoietic cluster of greater than 50 cells regardless of morphology. It is anticipated that ruxolitinib will decrease colony formation in a dose dependent fashion and perhaps predict for *in vivo* efficacy.

16.4 Genomic Studies

Using portion of cryopreserved bone marrow aspirates, 100ug of DNA will be isolated as previously described. Next, a comprehensive sequencing of subjects by NextGen sequencing of JAK2, c-CBL, N-RAS, K-RAS, RUNX-1, TET2, SRSF2, EZH2, ASXL1, and DNMT3a will be done in with pretreatment samples and end of study **or** progression. The isolated DNA will be sent to the laboratory of [name] located on the campus of Memorial Sloan Kettering Cancer Center. [name] has is a nationally recognized expert in the genomics of myeloid malignancies and has sequenced many patients for this comprehensive panel of gene mutations.

16.5 JAK2 mutations as a mechanism of Ruxolitinib resistance

Mutational status of JAK2 tyrosine kinase at time of progression by deep sequencing of JAK2 at pretreatment and at progression to include M929I, Y931C, G935R, R938L, I960V, E985K. Emerging reports have suggested mutations in JAK2 that may confer resistance to ruxolitinib. We will use samples from subjects taken at the above time, isolate DNA as previously described and amplify the JAK2 transcript by PCR. Next, gel extraction will be done and the entire JAK2 coding region will be sequenced at the H. Lee Moffitt Cancer Center molecular genomics core.

17 REGULATORY CONSIDERATIONS

This research will be done in compliance with the applicable State and Federal laws and regulations and in compliance with ICH guidelines. The study description will be posted on the www.clinicaltrials.gov website in compliance with current regulations. The data and safety plan will be executed in accordance with ICH guidelines and in compliance with policy and procedures at the H. Lee Moffitt Cancer Center and Research Institute. The

following must be observed to comply with Food and Drug Administration regulations for the conduct and monitoring of clinical investigations; they also represent sound research practice:

17.1 Informed Consent

The principles of informed consent are described by Federal Regulatory Guidelines (Federal Register Vol. 46, No. 17, January 27, 1981, part 50) and the Office for Protection from Research Risks Reports: Protection of Human Subjects (Code of Federal Regulations 45 CFR 46). They must be followed to comply with FDA regulations for the conduct and monitoring of clinical investigations.

17.2 Use of Specimens For Research

The patient is free at any time in the future to decide not to provide specimens or to withdraw his/her specimens from further scientific research. Such a decision will have UnoU impact on his/her treatment or other aspects of participation in this study.

17.3 Institutional Review

This study must be approved by an appropriate institutional review committee as defined by Federal Regulatory Guidelines (Ref. Federal Register Vol. 46, No. 17, January 27, 1981, part 56) and the Office for Protection from Research Risks Reports: Protection of Human Subjects (Code of Federal Regulations 45 CFR 46).

17.4 Drug Accountability

For each drug supplied for a study, an accountability ledger containing current and accurate inventory records covering receipt, dispensing, and the return of study drug supplies must be maintained. Drug supplies must be kept in a secure, limited access storage area under the recommended storage conditions. During the course of the study, the following information must be noted on the accountability ledger; the identification code of the subject to whom drug is dispensed, the date(s) and quantity of drug dispensed to the subject, and the date(s) and quantity of drug returned by the subject; subjects should return empty containers to the investigator, with the return noted on the ledger. These Accountability Forms must be readily available for inspection and are open to FDA inspection at any time.

17.5 RETENTION OF RECORDS

U.S. FDA regulations (21 CFR §312.62[c]) require that records and documents pertaining to the conduct of this study and the distribution of investigational drug,

including CRFs, consent forms, laboratory test results, and medication inventory records, must be retained by the Principal Investigator for 2 years after marketing application approval. If no application is filed, these records must be kept 2 years after the study is discontinued and the U.S. FDA and the applicable national and local health authorities are notified.

17.6 Study Monitoring:

As part of the responsibilities assumed by participating in the study, the Investigator agrees to maintain and have available for monitoring adequate case records (accurate source documents and CRFs) for the subjects treated under this protocol. In addition, the Investigator agrees to maintain all administrative documents, eg, IRB/IEC correspondence, investigational product and supplies shipment manifests, monitoring logs, or Moffitt Cancer Center/designee correspondence. The PI will be primarily responsible for monitoring of adverse events, protocol violations, and other immediate protocol issues. The study coordinator will collect information of subjects enrolled at Moffitt and other institutions through the use of electronic or paper AE forms, CRF forms, End of Study forms, and Informed Consent forms.

Internal Monitoring

Data will be captured in Oncore, Moffitt's Clinical Trials Database. The Case Report Forms will be reviewed by Moffitt's Internal Monitors, periodically, throughout the conduct of the trial. The monitoring will include source data verification, utilizing research subjects' medical records.

On-site Audits

The Investigator should promptly notify Moffitt Cancer Center or its authorized representative of any audits scheduled by any regulatory authorities and promptly forward copies of any audit reports received to Moffitt Cancer Center or its authorized representative.

Data & Safety Monitoring Plan

Identification of oversight responsibility:

The PI has primary responsibility.

The MCC Protocol Monitoring Committee (PMC);

The PMC meets monthly and reviews accrual, patterns and frequencies of all adverse

events, protocol violations and when applicable, internal audit results.

Description of internal (PI) safety review and monitoring process:

Responsible for identifying and reviewing adverse events biweekly:

Principal Investigator

Study team

To be reviewed:

Adverse events by grade (Gr. 3 or above using CTCAE v4.0) and attribution (expected or unexpected)

Relationship to study drug/intervention

Application of dose finding escalation/de-escalation rules

Application of study designed stopping/decision rules

Whether the study accrual pattern warrants continuation/action

Protocol violations

[figure not shown]
AEs will be reported along with all other data in the Oncore database. The PI or PI designate will report all adverse events to the Clinical Research Office (CRO). The CRO will report all SAEs to INCYTE, and all reportable SAEs to the IRB. AE information will be entered into the CRO database. AE information will be managed by the CRO and will be made available to the PMC or appropriate monitoring body by designated members of the PMC or the study statisticians.

19 APPENDIX A

Performance Status Criteria

ECC	G Performance Status Scale	Karnofsky Performance Scale			
Grade	Descriptions	Percent	Description		
0	Normal activity. Fully active, able to carry on all pre-disease	100	Normal, no complaints, no evidence of disease.		
0	performance without restriction.	90	Able to carry on normal activity; minor signs or symptoms of disease.		
1	Symptoms, but ambulatory. Restricted in physically strenuous activity, but ambulatory and able	80	Normal activity with effort; some signs or symptoms of disease.		
1	to carry out work of a light or sedentary nature (e.g., light housework, office work).	70	Cares for self, unable to carry on normal activity or to do active work.		
2	In bed <50% of the time. Ambulatory and capable of all self-care, but unable to carry out	60	Requires occasional assistance, but is able to care for most of his/her needs.		
	any work activities. Up and about more than 50% of waking hours.	50	Requires considerable assistance and frequent medical care.		
3	In bed >50% of the time. Capable of only limited self-care, confined	40	Disabled, requires special care and assistance.		
3	to bed or chair more than 50% of waking hours.	30	Severely disabled, hospitalization indicated. Death not imminent.		
4	100% bedridden. Completely disabled. Cannot carry on any	20	Very sick, hospitalization indicated. Death not imminent.		
4	self-care. Totally confined to bed or chair.	10	Moribund, fatal processes progressing rapidly.		
5	Dead.	0	Dead.		

20 APPENDIX B

RESPONSE CRITERIA FOR SUBJECTS WITH CMML ACCORDING IWG 2006 CRITERIA

ALTERING DISEASE NATURA	AL HISTORY						
Complete remission (CR)	Bone marrow: ≤ 5% myeloblasts with normal maturation of all cell lines						
()	Persistent dysplasia will be noted						
	Peripheral blood:						
	Hemoglobin ≥ 11 g/dL						
	Platelets $\geq 100 \times 10^9 / L$						
	Neutrophils $\geq 1.0 \times 10^9/L$						
	Blasts 0%						
Partial remission (PR)	All CR criteria if abnormal before treatment, except:						
· · · · · ·	Bone marrow blasts decreased by $\geq 50\%$ over pretreatment but still $> 5\%$						
	Cellularity and morphology not relevant						
Marrow CR	Bone marrow: $\leq 5\%$ myeloblasts and decrease by $\geq 50\%$ over pretreatment						
	Peripheral blood: if HI responses, they will be noted in addition to marrow CR						
Stable disease (SD)	Failure to achieve at least PR, but no evidence of progression for > 8 weeks						
Failure	Death during treatment						
	Disease progression characterized by worsening of cytopenias, increase in % of						
	bone marrow blasts, or progression to a more advanced MDS FAB subtype than						
	pretreatment						
Disease Progression (PD)	For subjects with:						
	Less than 5% blasts: $\geq 50\%$ increase in blasts to $\geq 5\%$						
	blasts						
	5%-10% blasts: \geq 50% increase in blasts to \geq 10% blasts						
	10%-20% blasts: \geq 50% increase in blasts to \geq 20%						
	blasts						
	20%-30% blasts: $\geq 50\%$ increase in blasts to $\geq 30\%$						
	blasts						
	Any of the following:						
	At least 50% decrement from maximum						
	remission/response levels in granulocytes or platelets						
	Reduction in hemoglobin (Hgb) concentration by ≥ 2 g/dL						
CHECKENETIC PECPONCE	- Transfusion dependence						
CYTOGENETIC RESPONSE							
Complete	Disappearance of the chromosomal abnormality without appearance of new ones						
Partial At least 50% reduction of the chromosomal abnormality							
HEMATOLOGICAL IMPROVEMENT (HI)							
Erythroid response (HI-E)	Hgb increase by $\geq 1.5 \text{ g/dL}$						
(Pretreatment < 11 g/dL)	Relevant reduction of units of RBC transfusions by an absolute number of at						
	least 4 RBC transfusions/8 weeks compared with the pretreatment transfusion						
	number in the previous 8 weeks. Only RBC transfusions given for a Hgb of ≤						
District magnency (III D)	9.0 g/dL pretreatment will count in the RBC transfusion evaluation Platelet response (HI-P) Absolute increase of $\geq 30 \times 10^9$ /L for subjects starting with $\geq 20 \times 10^9$ /L						
Platelet response (HI-P) (Pretreatment < 100 x 10 ⁹ /L)	Absolute increase of $\ge 30 \times 10^{7}$ L for subjects starting with $\ge 20 \times 10^{7}$ L Increase from $< 20 \times 10^{9}$ /L to $\ge 20 \times 10^{9}$ /L and by at least 100%						
	At least 100% increase and an absolute increase of > 0.5 x 10 ⁹ /L						
Neutrophil response (HI-N)	At least 100% increase and an absolute increase of > 0.5 x 10 /L						
(Pretreatment $< 1.0 \times 10^9/L$)							

PROGRESSION/RELAPSE CRITERIA FOR SUBJECTS WITH CMML

ALTERING DISEASE NAT	URAL HISTORY					
Disease Progression (PD)	For subjects with:					
	Less than 5% blasts: \geq 50% increase in blasts to $>$					
	5% blasts					
	5%-10% blasts: \geq 50% increase in blasts to \geq 10%					
	blasts					
	10%-20% blasts: \geq 50% increase in blasts to \geq 20%					
	blasts					
	20%-30% blasts: \geq 50% increase in blasts to \geq 30%					
	blasts					
	Any of the following:					
	At least 50% decrement from maximum					
	remission/response levels in granulocytes or					
	platelets					
	Reduction in hemoglobin (Hgb) concentration by ≥					
	2 g/dL					
Disease transformation	Transfusion dependence					
	Transformation to AML (30% or more blasts)					
Relapse after CR or PR	At least one of the following:					
	Return to pretreatment bone marrow blast % Decrement of ≥ 50% from maximum					
	remission/response levels in granulocytes or					
	platelets					
	- Reduction in Hgb concentration by ≥ 1.5 g/dL or transfusion					
	dependence					
HEMATOLOGICAL IMPR						
Progression/relapse after HI	At least one of the following:					
	At least 50% decrement from maximum response					
	levels in granulocytes or platelets					
	Reduction in Hgb by $\geq 1.5 \text{ g/dL}$					
	- Transfusion dependence					

21 APPENDIX C: CYP3A4 Strong Inhibitors

HIV Antivirals:

- -indinavir
- -boceprevir
- -lopinavir/ritonavir
- -ritonavir
- -telaprevir
- -nelfinavir
- -saquinavir

Others:

- -clarithromycin
- -conivaptan
- -grapefruit juice
- -mibefradil
- -posaconazole
- -voriconazole
- -itraconazole
- -ketoconazole
- -nefazodone
- -telithromycin

^{*} Dose reductions as in section 7 are required for strong inhibitors of the CYP3A4.

22 APPENDIX D: Myeloproliferative Neoplasms-Symptom Assesment Form (MPN-SAF)

The Myelofibrosis Symptom Assessment Form (MPN-SAF) Validation Survey.

Instructions: Please fill out all questions, as best able, until the STOP instruction toward the end of the packet.

Brief Fatigue Inventory @

Instructions: Please fill out all questions, as best able, reflecting how these symptoms affected you over the LAST WEEK unless directed otherwise. Complete forms until the STOP instruction toward the end of the packet.

Symptom	1 to 10 (0 if absent) ranking* 1 is most favorable and 10 least favorable						
Please rate your fatigue (weariness, tiredness) by circling the one number that best describes your fatigue right NOW	(No Fatigue) 0 1 2 3 4 5 6 7 8 9 10 (Worst Imaginable)						
Please rate your fatigue (weariness, tiredness) by circling the one number that best describes your USUAL level of fatigue during past 24 hours	(No Fatigue) 0 1 2 3 4 5 6 7 8 9 10 (Worst Imaginable)						
Please rate your fatigue (weariness, tiredness) by circling the one number that best describes your WORST level of fatigue during past 24 hours	(No Fatigue) 0 1 2 3 4 5 6 7 8 9 10 (Worst Imaginable)						
Circle the one number that	describes how, during the past 24 hours, fatigue has interfered with your						
General activity	(Does not Interfere) 0 1 2 3 4 5 6 7 8 9 10 (Completely Interferes)						
• Mood	(Does not Interfere) 0 1 2 3 4 5 6 7 8 9 10 (Completely Interferes)						
Walking ability	(Does not Interfere) 0 1 2 3 4 5 6 7 8 9 10 (Completely Interferes)						
 Normal work (includes work both outside the home and daily chores) 	(Does not Interfere) 0 1 2 3 4 5 6 7 8 9 10 (Completely Interferes)						
Relations with other people	(Does not Interfere) 0 1 2 3 4 5 6 7 8 9 10 (Completely Interferes)						
Enjoyment of life	(Does not Interfere) 0 1 2 3 4 5 6 7 8 9 10 (Completely Interferes)						

@ MD Anderson Cancer Center

Figure 1.The Myelofibrosis Symptom Assessment Form (MPN-SAF) Validation Survey.

Circle the one number that describes how, during the past Week how much difficulty you have had with each of the following symptoms						
(Absent) 0 1 2 3 4 5 6 7 8 9 10 (Worst Imaginable)						
(Absent) 0 1 2 3 4 5 6 7 8 9 10 (Worst Imaginable)						
(Absent) 0 1 2 3 4 5 6 7 8 9 10 (Worst Imaginable)						
(Absent) 0 1 2 3 4 5 6 7 8 9 10 (Worst Imaginable)						
(Absent) 0 1 2 3 4 5 6 7 8 9 10 (Worst Imaginable)						
(Absent) 0 1 2 3 4 5 6 7 8 9 10 (Worst Imaginable)						
(Absent) 0 1 2 3 4 5 6 7 8 9 10 (Worst Imaginable)						
(Absent) 0 1 2 3 4 5 6 7 8 9 10 (Worst Imaginable)						
(Absent) 0 1 2 3 4 5 6 7 8 9 10 (Worst Imaginable)						
(Absent) 0 1 2 3 4 5 6 7 8 9 10 (Worst Imaginable)						
(Absent) 0 1 2 3 4 5 6 7 8 9 10 (Worst Imaginable)						
(Absent) 0 1 2 3 4 5 6 7 8 9 10 (Worst Imaginable)						
(Absent) 0 1 2 3 4 5 6 7 8 9 10 (Worst Imaginable)						
(Absent) 0 1 2 3 4 5 6 7 8 9 10 (Worst Imaginable)						
(Absent) 0 1 2 3 4 5 6 7 8 9 10 (Worst Imaginable)						
(Absent) 0 1 2 3 4 5 6 7 8 9 10 (Daily)						
(Absent) 0 1 2 3 4 5 6 7 8 9 10 (Worst Imaginable)						
(As good as it can be) 0 1 2 3 4 5 6 7 8 9 10 (As bad as it can be)						

[©] Mayo Clinic

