3 STUDY ENDPOINTS

3.1 Primary

- 3.1.1 The maximum tolerated dose (MTD) of ruxolitinib for the treatment of CMML. The MTD is defined as the highest dose where less than 33% of subjects experience a drug related predefined dose limited toxicity (DLT).
- 3.1.2 Proportion of subject achieving clinical benefit defined as hematologic improvement, complete remission, partial remission, or stable disease by the IWG 2006 criteria (see appendix B)

- 3.2 Secondary
- **3.2.1** Acute myeloid leukemia (AML) transformation according to WHO criteria.
- **3.2.2** Overall survival (OS).
- **3.2.3** Duration of response.
- 3.2.4 The Myeloproliferative Neoplasms Symptom Assessment Form (MPN-SAF) at baseline and at best response.
- 3.2.5 >50% decrease in splenic length as measured by physical exam if applicable
- **3.2.6** The suppression of pSTAT5 intracellular signaling after ruxolitinib in CMML subjects (pretreatment, at 1-2hr post treatment, cycle 2, cycle 4, and progression.)
- **3.2.7** Determine number of colonies formed in the presence of GM-CSF and/or ruxolitinib (pretreatment and progression) as a future predictor of response.
- 3.2.8 Mutational status in our CMML subjects by sanger sequencing of JAK2, c-CBL, N-RAS, K-RAS,RUNX-1, TET2, SRSF2, EZH2, ASXL1, and DNMT3a (pretreatment and progression).
- 3.2.9 Mutational status of JAK2 tyrosine kinase at time of progression by deep sequencing of JAK2 to include M929I, Y931C, G935R, R938L, I960V, E985K. (pretreatment and at progression)

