9.3 Subject Withdrawal from Study Medication

If the subject is permanently withdrawn from treatment with study medication, but does not withdraw consent, the investigator must make every effort to have the subject complete all withdrawal assessments at the time of withdrawal, and complete all scheduled follow-up visits. Treatment with study medication must be discontinued if:

- The subject withdraws consent.
- Further participation would be injurious to the subject's health or well-being in the Investigator's medical judgment.

- The study is terminated.
- Marketing approval of CMML
- The subject becomes pregnant
- The subjects exhibits leukemic transformation (as evidenced by bone marrow blast counts of at least 20%, or peripheral blast counts of at least 20% lasting at least 8 weeks.
- No clinical benefit has been attained after 16 weeks of treatment.
- Evidence of Disease progression according to IWG 2006 criteria.
- a subject experiences a DLT.
- a subject is significantly non-compliant with the requirements of the protocol.
- a subject has an adverse experience that would, in the investigator's judgment, make continued participation in the study an unacceptable risk.

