23 APPENDIX E: WHO CLASSIFICATION FOR CMML

WHO Subtype	Peripheral Blood	Bone Marrow
	*<5 percent blasts	*<10% myeloblast
	**<19 percent blasts	**<19 percent blasts
	persistant monocytosis >1000/ul	>10% dysplasia in
Chronic Myelomonocytic Leukemia	+/- cytopenias	affected lineage
*CMML-1	Leukocytosis frequent	**Auer Rods
**CMML-2		The absence of the
		Philadelphia
		chromosome of bcr-abl
		fusion gene.

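### Appendix B and Section 9.3 conflict on when rising blasts end stable disease, so one marrow can be both leukemic transformation and a primary-endpoint success

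*Combined protocol and SAP*

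**What the plan says.** - **Primary endpoint (3.1.2).** Success is "hematologic improvement, complete remission, partial remission, or stable disease by the IWG 2006 criteria".
- **Stable disease (Appendix B, repeated in Section 14).** "Failure to achieve at least PR, but no evidence of progression for > 8 weeks".
- **Disease progression (both tables of Appendix B).** For entry blasts of 10% to 20%, the blast row asks for a relative increase of at least 50% and a level of at least 20%. A list introduced by "Any of the following" adds three routes that do not use blasts: a fall of at least 50% in granulocytes or platelets from the best level, a hemoglobin fall of at least 2 g/dL, and transfusion dependence.
- **Failure (Appendix B, directly below stable disease).** "Disease progression characterized by worsening of cytopenias, increase in % of" marrow blasts, or a move to a more advanced FAB subtype. No size of increase is given.
- **Transformation (Appendix B, progression/relapse table).** "Transformation to AML (30% or more blasts"), with no relative-rise condition.
- **Withdrawal from study medication (9.3).** Treatment stops for leukemic transformation, shown by "bone marrow blast counts of at least 20%, or peripheral blast counts of at least 20% lasting at least 8 weeks". Progression by the IWG 2006 criteria is a separate item in the same list.
- **Entry (Appendix E).** CMML-2 is shown with "<19 percent blasts".
- **Timing (Section 13).** Marrows are due at weeks 8 and 16, with a 14-day window. Subjects who stop early have an end-of-treatment visit, including a marrow, within two weeks of the last dose.

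**The concern.** Stable disease is a success, and it depends on the absence of progression. The plan gives three different blast rules that could decide that absence: the progression row, the Failure row and the transformation row. A fourth rule, in 9.3, uses the name of the third with a different threshold. Nothing ranks them or links the 9.3 criterion to the scoring of response.

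If the progression row governs, a subject whose marrow has reached the level that 9.3 calls leukemic transformation can be reported as having clinical benefit on that same marrow. If the Failure row governs, the same marrow is a failure. Two assessors who follow the text could score one subject in opposite ways on the primary endpoint. The secondary endpoint of AML transformation (3.2.1) does not settle it: it refers to WHO criteria and gives no blast threshold.

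**Working it through.** **1. The plan's own figures.** Section 15.2 uses a Simon design: stop if 1 or fewer of 10 respond, and reject the drug if 5 or fewer of 29 respond. With X1 ~ Bin(10, p) and X2 ~ Bin(19, p), the probability of not rejecting the drug is the sum over x = 2 to 10 of P(X1 = x) × P(X2 ≥ 6 − x).
- At p = 0.10 it is 0.0471 (stated type I error 0.05).
- At p = 0.30 it is 0.8051, so type II error is 0.195 (stated 0.19).
- The probability of stopping early under the null is 0.7361 (stated 0.74).

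The design reproduces. The point concerns who is counted in it.

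**2. Blast level at which the progression row is met.** For entry blasts b between 10% and 20%, the threshold is max(20, 1.5 × b). It exceeds 20% once b > 20/1.5 = 13.3%.

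| Entry blasts b | Progression row met at | Values ≥ 20% that are not blast progression |
|---|---|---|
| 12% | 20% | none |
| 13.3% | 20% | none |
| 14% | 21% | 20% to <21% |
| 15% | 22.5% | 20% to <22.5% |
| 16% | 24% | 20% to <24% |
| 17% | 25.5% | 20% to <25.5% |
| 18% | 27% | 20% to <27% |
| approaching 19% | approaching 28.5% | 20% to <28.5% |

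The whole gap lies below Appendix B's 30%.

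**3. Two marrows put through each rule.**

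| Rule | 15% to 22% (22/15 = 1.47, a 47% rise) | 18% to 25% (25/18 = 1.39, a 39% rise) |
|---|---|---|
| 9.3 leukemic transformation (marrow ≥ 20%) | met | met |
| Appendix B progression, blast row | not met | not met |
| Appendix B transformation (≥ 30%) | not met | not met |
| Appendix B Failure, read literally | met | met |

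If no count, hemoglobin or transfusion criterion is met, the score depends on whether the progression row or the Failure row defines progression for stable disease.

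**4. When it matters.** Stable disease needs more than 8 weeks without progression. A marrow due at week 8 may fall after 8 weeks because of the 14-day window, and so may an early end-of-treatment marrow. On such a marrow, stable disease and the 9.3 criterion can be met together. A crossing seen only at week 16 is a different case. That subject may already hold stable disease as best response, and so may one who goes from 12% to 20% (20/12 = 1.67, a 67% rise, clear progression).

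**5. Size.** One subject among 29 is 1/29 = 3.4 points on the 3.1.2 proportion. The documents do not say how often this would occur. For the Simon rule, assume that it counts stable disease, that the true success rate is 10%, and that a further share m of subjects is scored as success through the gap:

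| m | 0 | 1% | 2% | 3% | 5% |
|---|---|---|---|---|---|
| P(drug not rejected) | 0.047 | 0.069 | 0.095 | 0.126 | 0.201 |

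These values of m are illustrative.

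**The case against.** The strongest reply is that Appendix B already covers these subjects. The Failure row mentions any increase in marrow blasts, so 15% to 22% is a failure as it stands. The non-blast routes will also catch many subjects whose disease is transforming. Both statements are fair, and they rule out the reading that the plan plainly scores such subjects as stable. They do not close the gap. Under the literal Failure row a change from 11% to 12% would also be progression, and the 50% condition in the progression row would then have no purpose.

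A second reply is that reconciling the two transformation thresholds is enough, because transformation is itself a row of Appendix B's progression table. This largely stands: with one threshold, 9.3 and Appendix B could no longer disagree about the same marrow, provided that row counts as evidence of progression for stable disease. The plan does not say so, which is why a scoring sentence is still needed. It would be wrong to infer that one cut-off would do nothing.

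A third reply is that stable disease followed later by AML is no contradiction, since the two describe different times. That is correct. The conflict is confined to a single marrow that serves both purposes.

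Finally, the 8-week duration in 9.3 might be read as applying to marrow blasts as well. The comma attaches it more naturally to peripheral blasts, but the text leaves room for doubt.

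**Conclusion.** The conflict is real and narrow. It concerns entry marrow blasts above 13.3% and below 19%, and on-treatment values from 20% to just under 1.5 times baseline. Each subject scored through it moves the 3.1.2 proportion by 3.4 points if the denominator is the 29 phase 2 subjects. The frequency is unknown.

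The finding assumes that the 9.3 marrow criterion needs no 8-week duration, that no other progression criterion is met, and that the deciding marrow falls after 8 weeks.

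A reader might infer that the trial's type I error is inflated. The documents do not establish that: Section 15.2 tests a response rate without saying whether stable disease counts, and Section 15.5 summarises complete platelet response. A reader might also extend the gap to all CMML-2 subjects or to entry at 19%. Neither follows: at or below 13.3% the 20% line already implies a 50% rise, and Appendix E as printed places 19% outside entry.

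**What to change.** 1. Reconcile the 20% in Section 9.3 and the 30% in Appendix B into one transformation criterion, used there and for endpoint 3.2.1. State whether the 8-week duration applies to marrow blasts. The value is for the clinical team to choose.
2. State in Appendix B whether the progression row or the Failure row defines progression for stable disease.
3. Add to Appendix B and Section 14: *A subject who meets the transformation criterion is scored as progression from the date of that assessment, whatever the relative rise in blasts. That assessment cannot support stable disease. Stable disease attained at an earlier assessment [is / is not] kept as best response.* The sponsor should settle the bracketed choice before response data are reviewed.

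The third item works only after the first, because the documents now hold two transformation criteria, and under the 30% row the sentence would change nothing within the gap. No new data or visits are needed. The cost is a stated clinical benefit rate that may be slightly lower.
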